1. VERSION HISTORY

Table 1. Summary of Changes

Version/ Date	Associated Protocol Amendment	Rationale	Specific Changes
1.0 19 Feb 2021	Original 28 Jan 2021	N/A	N/A
2.0 25 Aug 2021	Amendment 2 02 Jun 2021 Amendment 3 24 Jun 2021 PACL 14 Jul 2021	PART-4 was added to evaluate metabolism and excretion and other updates to be in-line with protocol amendment PART-5 was added to evaluate safety and tolerability of PF-07321332 at supratherapeutic exposure and other updates to be in-line with protocol amendment	
 Included PART-4 and PART-5 and removed the specification of PART-3 as optional in the description from the protocol (Section 2). Updated Figure 1 to include PART-4 and PART-5. Defined endpoints and baseline variables for PART-4 and PART-5 (Section 3). Defined an additional analysis set, the Excretion Analysis Set, for PART-4 (Section 4). Specified analysis methods for PART-4 and PART-5 (Section 6). Updated minor changes following table review.

2. INTRODUCTION

The current study is the first clinical administration with PF-07321332. It is a 5-part study combining **PART-1: SAD**, **PART-2: MAD**, **PART-3: relative bioavailability/food effect**, **PART-4: metabolism and excretion** and **PART-5 supratherapeutic exposure (SE)**. PART-1 and 2 are randomized, double-blind, sponsor-open, placebo-controlled trial to evaluate safety, tolerability and PK of single and multiple escalating oral doses of PF-07321332 in

*healthy adult participants and **PART-3** is a randomized open label study to evaluate relative bioavailability and food effect of an oral tablet formulation. **PART-2** of the study may also evaluate the safety tolerability and PK in Japanese participants. **PART-4** is an open-label, non-randomized, single period to evaluate the metabolism and excretion of PF-07321332. **PART-5** is a double-blind, sponsor-open, randomized, cross-over study to evaluate safety and tolerability at supratherapeutic exposures.*

This statistical analysis plan (SAP) provides the detailed methodology for summary and statistical analyses of the data collected in Study C4671001. This document may modify the plans outlined in the protocol; however, any major modifications of the primary endpoint definition or its analysis will also be reflected in a protocol amendment.

2.1. Study Objectives, Endpoints, and Estimands

There are no estimands for this study.

PART-1: SAD

Objectives	Estimands	Endpoints
Primary:	Primary:	Primary:

 To assess the safety and tolerability following a single dose of PF-07321332 alone or in combination with a PK boosting agent (ritonavir). 	N/A	
 Frequency, severity, and causal relationship of TEAEs and withdrawals due to TEAEs. Frequency and magnitude of abnormal laboratory findings. Changes from baseline in vital sign measurements and 12-lead ECG parameters.
Secondary:	Secondary:	Secondary:

 To assess the plasma PK profile of PF-07321332 following single ascending doses of PF-07321332 alone or in combination with a PK boosting agent (ritonavir) 	N/A	
 Plasma PK parameters of PF-07321332: 
 C_{max}, T_{max}, AUC_{last}, C_{max(dn)}, AUC_{last(dn)}. If data permits, AUC_{inf}, AUC_{inf(dn)}, t_{1/2}, V_{z/F}, and CL/F.
Tertiary/Exploratory:	Tertiary/Exploratory:	Tertiary/Exploratory:

 To explore metabolites in plasma, urine, and feces, if data permits. 	N/A	
 Qualitative characterization of metabolites of PF-07321332 in pooled plasma, urine, and feces as data permits.

 Quantitative excretion of drug-related material using ¹⁹F-NMR spectroscopy, if data permits. 	N/A	
 Total excretion of drug-related material in urine and feces separately, and both routes combined, expressed as a percent of total dose administered, if data permits.

 To determine the oral bioavailability of a tablet formulation of PF-07321332 relative to suspension, if evaluated (Optional) 	N/A	
 The ratio of AUC_{last}, AUC_{inf} and C_{max} of tablet formulation and suspension.

 To evaluate the effect of food (high fat meal) on the exposure of PF-07321332 following a single oral dose of PF-07321332 tablet formulation, if evaluated (Optional) 	N/A	
 The ratio of AUC_{last}, AUC_{inf} and C_{max} of tablet formulation under fed condition and fasted condition.

PART-2: MAD (including optional Japanese cohort)

Objectives	Estimand	Endpoints
Primary:	Primary:	Primary:

 To assess the safety and tolerability following multiple ascending doses of PF-07321332 alone or in combination with a PK boosting agent (ritonavir). 	N/A	
 Frequency, severity, and causal relationship of TEAEs and withdrawals due to TEAEs. Frequency and magnitude of abnormal laboratory findings. Changes from baseline in vital sign measurements and 12-lead ECG parameters.
Secondary:	Secondary:	Secondary:

 To assess the plasma PK profile of PF-07321332 on Days 1, 5 and 10 following multiple ascending doses of PF-07321332 alone or in combination with a PK boosting agent (ritonavir). 	N/A	
 Plasma PK parameters of PF-07321332: 
 C_{max}, T_{max}, AUC_{tau} (where $tau=8$ hours for TID dosing or 12 hours for BID dosing), C_{min}, $C_{max}(dn)$, $AUC_{tau}(dn)$, C_{av}, R_{ac}, $R_{ac,Cmax}$, PTR, CL/F and V_z/F. If data permit, $t_{1/2}$.

 To assess the urinary PK profile of PF-07321332 on Day 10 following multiple ascending doses of PF-07321332 alone or in combination with a PK boosting agent (ritonavir). 	N/A	
 PF-07321332 urinary PK parameters: 
 Ae_{tau} and $Ae_{tau}\%$, CL
Tertiary/Exploratory:	Tertiary/Exploratory:	Tertiary/Exploratory:

 To explore metabolites in plasma if data permits. 	N/A	
 Qualitative characterization of metabolites of PF-07321332 in pooled plasma if data permits.

 To explore PK by microsampling technique(s), if evaluated (Optional). 	N/A	
 Concentration of PF-07321332, if evaluated.

PART-3: Relative Bioavailability/Food Effect Cohort

Objectives	Estimands	Endpoints
Primary:	Primary:	Primary:

 To determine the oral bioavailability of a tablet formulation of PF-07321332 relative to suspension. 	N/A	
 The ratio of AUC_{last}, AUC_{inf} and C_{max} of tablet formulation and suspension.
Secondary:	Secondary:	Secondary:

 To evaluate the effect of food (high-fat high-calorie meal) on the exposure of PF-07321332 following a single oral dose of PF-07321332 tablet formulation. 	N/A	
 The ratio of AUC_{last}, AUC_{inf} and C_{max} of tablet formulation under fed condition and fasted condition.

 To determine the pharmacokinetics of PF-07321332 following oral administration of tablet and suspension of PF-07321332. 	N/A	
 Plasma PK parameters of PF-07321332: T_{max}, C_{max}, AUC_{last}, $C_{max}(dn)$, $AUC_{last}(dn)$, if data permits AUC_{inf}, $AUC_{inf}(dn)$, $t_{1/2}$, CL/F, V_z/F.

 To determine the safety and tolerability of PF-07321332 following oral administration of tablet and suspension of PF-07321332. 	N/A	
 Frequency, severity, and causal relationship of TEAEs and withdrawals due to TEAEs. Frequency and magnitude of abnormal laboratory findings. Changes from baseline in vital sign measurements and 12-lead ECG parameters.
CCI		

PART-4: Metabolism and Excretion

Objectives	Estimands	Endpoints
Primary:	Primary:	Primary:

 To determine the extent of excretion of drug related material in urine and feces after a single oral administration of PF-07321332 with PK boosting agent ritonavir. 	N/A	
 Total recovery of drug related material in urine and feces separately, and both routes combined, expressed as a percent of total oral dose administered.
Secondary:	Secondary:	Secondary:

 To determine the pharmacokinetics of PF-07321332 following oral administration of PF-07321332 with PK boosting agent ritonavir. 	N/A	
 Plasma PK parameters of PF-07321332: T_{max}, C_{max}, AUC_{last}, if data permit AUC_{inf}, $t_{1/2}$, CL/F, V_z/F.

 To determine the safety and tolerability of PF-07321332 after a single oral administration of PF-07321332 with PK boosting agent ritonavir. 	N/A	
 Frequency, severity, and causal relationship of TEAEs and withdrawals due to TEAEs. Frequency and magnitude of abnormal laboratory findings. Changes from baseline in vital signs measurements and 12-lead ECG parameters.
Tertiary/Exploratory:	Tertiary/Exploratory:	Tertiary/Exploratory:

 To characterize the metabolic profile and identify circulating and excreted metabolites following administration of a single oral dose of PF-07321332 with PK boosting agent ritonavir, if possible. 	N/A	
 Metabolic profiling/identification and determination of relative abundance of PF-07321332 and the metabolites of PF-07321332 in plasma, urine, and feces, if possible.

PART-5: Supratherapeutic Exposure (NH CRU only)

Objectives	Estimands	Endpoints
Primary:	Primary:	Primary:

 To assess the safety and tolerability of a supratherapeutic exposure of PF-07321332 with a PK boosting agent (ritonavir) administered as split dosing. 	N/A	
 Frequency, severity, and causal relationship of TEAEs and withdrawals due to AEs. Frequency and magnitude of abnormal laboratory findings. Changes from baseline in vital sign measurements and 12-lead ECG parameters
Secondary:	Secondary:	Secondary:

 To assess the plasma PK of PF-07321332 at a supratherapeutic exposure of PF-07321332 with a PK boosting agent (ritonavir) administered as split dosing. 	N/A	
 Plasma PK parameters of PF-07321332: 
 C_{max}, T_{max}, AUC_{last} If data permit, AUC_{inf}, $t_{1/2}$.

2.2. Study Design

2.2.1. Overall Design

The study will combine **PART-1**: single ascending dose (SAD), **PART-2**: multiple ascending dose (MAD, including optional Japanese cohort), **PART-3**: relative bioavailability and food effect cohort, **PART-4**: metabolism and excretion study, and **PART-5**: supratherapeutic exposure cohort. **PART-1** and **PART-2** are randomized, double-blind (participant and investigator blinded), sponsor open, placebo controlled, single and multiple dose escalation study. **PART-3** is a randomized open label study to evaluate relative bioavailability and food effect. **PART-4** is an open-label, non-randomized, single period to evaluate the metabolism and excretion of PF-07321332. **PART-5** is a double-blind, sponsor open, randomized, cross-over study to evaluate safety and tolerability at supratherapeutic exposures to be conducted at NH CRU only.

2.2.2. PART-1: SAD

SAD will include 2 interleaving cohorts with a total of approximately 12 participants planned (approximately 6 participants in each cohort), with 4-period cross-over in each cohort. Period 3 and 4 are optional periods which may be used to further explore PK at additional doses or PK in combination with ritonavir or relative bioavailability of a new formulation or food effect (high-fat high-calorie meal), etc, based on emerging safety, tolerability and PK assessments.

There will be a washout interval of ≥ 5 days between dosing to a given participant. Participants will be required to stay at the CRU for the duration of the washout interval. However, they may be released at the discretion of the investigator. The washout interval may be adjusted based on data emerging from previous cohorts/periods.

2.2.3. PART-2: MAD

*The first MAD cohort may start after a same total daily dose, which provides comparable or higher total daily exposure (24 h) in SAD than the projected total daily steady-state exposure (over 24 h) at the starting dose in MAD, is found safe and well tolerated in **PART-1** of the study. The proposed MAD study design will be parallel cohorts, with 10 days of dosing. **PART-2** will consist of approximately 2 to 5 cohorts including up to 3 optional cohorts (cohorts 5, 6 and 7) with approximately 6 participants in each cohort. Cohort 7 is an optional Japanese participants cohort.*

2.2.4. PART-3: RBA and Food effect

This cohort will be an open label, randomized, 3-period, 3-sequence cross-over single dose cohort evaluating the relative bioavailability of PF-07321332 tablet compared to PF-07321332 oral suspension and to evaluate the effect of food on the bioavailability of the PF-07321332 tablet in healthy adult participants. A maximum of 18 participants may be enrolled in PART-3 of the study with approximately equal number of participants randomized to each sequence. There will be a wash-out period of at least 2 days between dosing in each period. Participants will be required to stay at the CRU until discharge in the last period. The washout interval may be adjusted based on data emerging from SAD and MAD cohorts.

2.2.5. PART-4: Metabolism and Excretion

This part will include a single cohort of approximately 6 male participants with at least 4 completers. All participants will receive 4 doses of 100 mg ritonavir as specified in the SoA. Each participant will receive a single dose of 300 mg of PF-07321332 on Day 1 0h along with 100 mg of ritonavir after at least 10h of fasting. The participants will be discharged on Day 11.

*In **PART-1** and **PART-2**, treatment sequences, actual doses, dose increments and dosing regimen may be adjusted, and intermediate or alternative dose levels may be substituted during the study based on emerging safety, tolerability, and PK data.*

[figure not shown]
2.2.6. PART-5: Supratherapeutic Exposure (NH CRU only)

This cohort will include up to 12 participants in a 4-period (Periods 3 and 4 are optional), double-blind, sponsor-open, randomized, 2-sequence, cross-over design to explore safety, tolerability and PK at supratherapeutic exposure. For each period, participants will receive split dosing administration (3 doses) of PF-07321332 or placebo at short intervals (approximately 2 h of the previous dose) after at least 2 hours after the breakfast on Day 1. Baseline ECGs, vitals and safety labs will be collected before breakfast. The first 2 periods will be a cross-over where participants will be given PF-07321332 at 0, 2 and 4 hours at the dose of 750 mg (or placebo) with ritonavir. Periods 3 and 4 (if conducted) will only be conducted if supratherapeutic concentrations are not reached in Period 1. In periods 3 and 4 (if conducted) doses may be given up to 4 times for a total daily dose not exceeding 3000 mg, with or without food.

2.2.7. Number of Participants

A total of up to 78 participants (12 in **PART-1: SAD**, up to 30 [with 2 cohorts and 3 optional cohorts] in **PART-2: MAD**, a maximum of 18 in **PART-3: Relative Bioavailability/Food Effect cohort**, 6 participants in **PART-4: Metabolism and Excretion cohort**, and up to 12 participants in **PART-5: Supratherapeutic Exposure**) are planned to be randomized in this study. At the discretion of the sponsor and investigator, participant who were enrolled in **PART-2** may be enrolled in **PART-5**.

Figure 1. C4671001 Study Design

*Optional dose levels in SAD/MAD may be used to explore higher doses or food effect or relative bioavailability or in combination with ritonavir (see more details in Section 4.1 of the protocol). Dosing with food may be done in one or more cohorts in SAD/MAD based on the emerging PK/safety data. **PART-4: Metabolism and Excretion (M&E)** is an open-label single dose cohort (see more details in Section 4.1 of the protocol). **PART-5: supratherapeutic exposure (SE)** is a double-blind, sponsor-open, randomized, cross-over cohort (see more details in Section 4.1 of the protocol).

SAD dose levels D1 to D8 and MAD dosing regimens DR1 to DR4 are listed in Table 9 and Table 10, respectively in Section 4.3 of the protocol.

3. ENDPOINTS AND BASELINE VARIABLES: DEFINITIONS AND CONVENTIONS

3.1. Primary Endpoint(s)

As listed in Section 2.1 the primary endpoints in PART-1, PART-2, and PART-5 are related to safety/tolerability and are described in Section 3.5.

The primary endpoints in PART-3 are the plasma PK endpoints which are described in Section 3.3.

The primary endpoints in PART-4 are percent recovery and cumulative recovery of drug-related material in urine, feces determined based on total administered dose. Percent recovery of drug-related material in urine and feces will be determined based on total administered dose.

3.2. Secondary Endpoint(s)

The secondary endpoints in PART-1, PART-2, PART-4 and PART-5 related to PK are described in Section 3.3. The secondary endpoints in PART-3 and PART-4 related to safety/tolerability are described in Section 3.5.

3.3. Other Endpoint(s)

3.3.1. Pharmacokinetic (PK) Endpoints

Blood and urine samples for the PK analysis of PF-07321332 will be taken according to the SoA given in the protocol.

The PK parameters of PF-07321332 to be derived (if data permit) from the concentration-time data using standard noncompartmental methods are defined in [Table 2](#) (single oral dose) and [Table 3](#) (multiple oral doses). Urine PF-07321332 PK parameters are described in [Table 3](#). Actual PK sampling times will be used in the derivation of PK parameters. In the case that actual PK sampling times are not available, nominal PK sampling time will be used in the derivation of PK parameters.

Table 2. Noncompartmental PK Parameters for PART-1: Single Ascending Doses, PART-3: Relative Bioavailability/Food Effect Cohort, PART-4: Metabolism and Excretion Cohort and PART-5: Supratherapeutic Exposure Cohort

Parameter	Analysis Scale	PF-07321332
AUC_{last}^{\dagger}	ln	D, A
AUC_{inf}^*	ln	D, A
C_{max}	ln	D, A
T_{max}	R	D
$t_{1/2}^*$	R	D
$CL/F^{\$}$	ln	D
$V_z/F^{\$}$	ln	D
$AUC_{last(dn)}^{\ddagger}$	ln	D
$AUC_{inf(dn)}^{*\ddagger}$	ln	D
$C_{max(dn)}^{\ddagger}$	ln	D

Key: D=displayed with descriptive statistics,
 ln=natural-log transformed, R=raw (untransformed), A=analysed
 *=if data permits, dn = normalized to a 1mg PF-07321332 dose,
 †=In PART-3, pre-dose (0h) sample from Periods 2 and 3 will also be considered as 48h PK sample for Periods 1 and 2, respectively,
 ‡=Not PART-4 or PART-5,
 \\$=Not PART-5.

T_{last} will also be provided as a support parameter for AUC_{last} . T_{last} values will only be listed and not summarized.

Table 3. Noncompartmental PK Parameters for PART-2: Multiple Ascending Dose

Parameter	Analysis Scale	PF-07321332
Plasma		
AUC_{τ}	ln	D
C_{max}	ln	D
T_{max}	R	D
C_{min}	R	D
C_{av}	ln	D
R_{ac}	ln	D
$R_{ac,Cmax}$	ln	D
PTR	ln	D
CL/F	ln	D
$t_{1/2}^*$	R	D
V_z/F^*	ln	D
$AUC_{\tau(dn)}$	ln	D
$C_{max(dn)}$	ln	D
Urine		
Ae_{τ}	R	D
$Ae_{\tau}\%$	R	D
CL_r	R	D

Key: D=displayed with descriptive statistics,
 ln=natural-log transformed, R=raw (untransformed),
 *=if data permits, dn = normalized to a 1mg PF-07321332 dose.

3.4. Baseline Variables

Baseline variables are those collected on Day 1 prior to dosing or before Day 1. Baseline for laboratory data, vital signs and ECG are defined in Sections 3.5.2, 3.5.3 and [3.5.4](#) respectively.

3.5. Safety Endpoints

3.5.1. Adverse Events

An adverse event is considered a Treatment-Emergent Adverse Event (TEAE) if the event started during the effective duration of treatment. All events that start on or after the first dosing day and time/start time, if collected, but before the end of the study will be flagged as TEAEs. The algorithm will not consider any events that started prior to the first dose date.

A 3-tier approach for summarizing AEs will not be used due to the low number of participants planned to be recruited.

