### 8. STUDY ASSESSMENTS AND PROCEDURES

The investigator (or an appropriate delegate at the investigator site) must obtain a signed and dated ICD before performing any study-specific procedures.

Study procedures and their timing are summarized in the SoA. Protocol waivers or exemptions are not allowed.

Safety issues should be discussed with the sponsor immediately upon occurrence or awareness to determine whether the participant should continue or discontinue study intervention.

Adherence to the study design requirements, including those specified in the SoA, is essential and required for study conduct.

All screening evaluations must be completed and reviewed to confirm that potential participants meet all eligibility criteria. The investigator will maintain a screening log to record details of all participants screened and to confirm eligibility or record reasons for screening failure, as applicable.

Participants will be screened within 28 days prior to administration of the study intervention to confirm that they meet the study population criteria for the study. If the time between screening and dosing exceeds 28 days as a result of unexpected delays (eg, delayed drug shipment), then participants do not require rescreening if the laboratory results obtained prior to first dose administration meet eligibility criteria.

A participant who qualified for this protocol but did not enroll from an earlier cohort/group may be used in a subsequent cohort/group without rescreening, provided laboratory results obtained prior to the first dose administration meet eligibility criteria for this study. In addition, other clinical assessments or specimen collections, eg, banked biospecimens, may be used without repeat collection, as appropriate.

Every effort should be made to ensure that protocol-required tests and procedures are completed as described. However, it is anticipated that from time to time there may be circumstances outside the control of the investigator that may make it unfeasible to perform the test. In these cases, the investigator must take all steps necessary to ensure the safety and well-being of the participant. When a protocol-required test cannot be performed, the investigator will document the reason for the missed test and any corrective and preventive actions that he or she has taken to ensure that required processes are adhered to as soon as possible. The study team must be informed of these incidents in a timely manner.

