## 8.3.1. Time Period and Frequency for Collecting AE and SAE Information

The time period for actively eliciting and collecting AEs and SAEs ("active collection period") for each participant begins from the time the participant provides informed consent, which is obtained before the participant's participation in the study (ie, before undergoing any study-related procedure and/or receiving study intervention), through and including a minimum of 28 calendar days after the last administration of the study intervention.

Follow-up by the investigator continues throughout and after the active collection period and until the AE or SAE or its sequelae resolve or stabilize at a level acceptable to the investigator and Pfizer concurs with that assessment.

For participants who are screen failures, the active collection period ends when screen failure status is determined.

If the participant withdraws from the study and also withdraws consent for the collection of future information, the active collection period ends when consent is withdrawn.

If a participant definitively discontinues or temporarily discontinues study intervention because of an AE or SAE, the AE or SAE must be recorded on the CRF and the SAE reported using the CT SAE Report Form.

Investigators are not obligated to actively seek AE or SAE after the participant has concluded study participation. However, if the investigator learns of any SAE, including a death, at any time after a participant has completed the study, and he/she considers the event to be reasonably related to the study intervention, the investigator must promptly report the SAE to Pfizer using the CT SAE Report Form.

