#### **Events Meeting the AE Definition**

- Any abnormal laboratory test results (hematology, clinical chemistry, or urinalysis)
  or other safety assessments (eg, ECG, radiological scans, vital sign measurements),
  including those that worsen from baseline, considered clinically significant in the
  medical and scientific judgment of the investigator. Any abnormal laboratory test
  results that meet any of the conditions below must be recorded as an AE:
  - Is associated with accompanying symptoms;
  - Requires additional diagnostic testing or medical/surgical intervention;
  - Leads to a change in study dosing (outside of any protocol-specified dose adjustments) or discontinuation from the study, significant additional concomitant drug treatment, or other therapy.
- Exacerbation of a chronic or intermittent preexisting condition including either an increase in frequency and/or intensity of the condition.
- New conditions detected or diagnosed after study intervention administration even though it may have been present before the start of the study.
- Signs, symptoms, or the clinical sequelae of a suspected drug-drug interaction.
- Signs, symptoms, or the clinical sequelae of a suspected overdose of either study intervention or a concomitant medication. Overdose per se will not be reported as an AE/SAE unless it is an intentional overdose taken with possible suicidal/self-harming intent. Such overdoses should be reported regardless of sequelae.

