#### Follow-up of AEs and SAEs

- The investigator is obligated to perform or arrange for the conduct of supplemental measurements and/or evaluations as medically indicated or as requested by the sponsor to elucidate the nature and/or causality of the AE or SAE as fully as possible. This may include additional laboratory tests or investigations, histopathological examinations, or consultation with other healthcare providers.
- If a participant dies during participation in the study or during a recognized follow-up period, the investigator will provide Pfizer Safety with a copy of any postmortem findings including histopathology.
- New or updated information will be recorded in the originally completed CRF.
- The investigator will submit any updated SAE data to the sponsor within 24 hours of receipt of the information.

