6.1. Primary Endpoint(s)

The primary endpoints in PART-1, PART-2 and PART-5 are related to safety/tolerability and their analyses are described Section 6.6.

The primary endpoints in PART-3 are the plasma PK endpoints whose analyses are described in Section 6.2.

The primary endpoints in PART-4 are percent recovery and cumulative recovery of drug-related material in urine, feces based on total administered dose. This will be calculated and reported separately.

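### The SAP's start-date rule for treatment-emergent adverse events can leave out a recorded pre-dose event that worsens after dosing

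*SAP*

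**What the plan says.** SAP Section 3.5.1 is the operative definition. It flags "All events that start on or after the first dosing day and time/start time, if collected, but before the end of the study" and then adds: "The algorithm will not consider any events that started prior to the first dose date". Neither sentence refers to a change in severity or seriousness. SAP Section 6.6.1, on adverse event reporting, refers only to the sponsor's reporting standards, which are not part of the documents.

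The flag feeds the endpoint "Frequency, severity, and causal relationship of TEAEs and withdrawals due to TEAEs" (SAP Section 2.1). SAP Section 6.1 states: "The primary endpoints in PART-1, PART-2 and PART-5 are related to safety/tolerability". PART-3 and PART-4 carry the same TEAE endpoint at secondary level.

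Three protocol provisions decide which events reach the algorithm and with what start date:

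- Section 8.3.1: active collection "begins from the time the participant provides informed consent".
- Appendix 3, Section 10.3.1: an adverse event includes "Exacerbation of a chronic or intermittent preexisting condition including either an increase in frequency and/or intensity of the condition".
- Appendix 3, Section 10.3.3, on follow-up of events already reported: "New or updated information will be recorded in the originally completed CRF".

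**The concern.** Collection starts at consent, and Section 8 of the protocol allows a gap of up to four weeks before dosing: "Participants will be screened within 28 days prior to administration of the study intervention". Some events will therefore be on the CRF before anyone is dosed. Mild symptoms just before dosing are plausible, because participants are confined from Day -1 and must stop caffeine and nicotine 24 hours before dosing (Protocol Section 5.3.2).

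Suppose a participant has a mild headache recorded on Day -1 that becomes severe after dosing. If the site updates the existing record, the start date stays before the first dose and the algorithm passes over the event. The post-dose severity, and any withdrawal it leads to, then drops out of an endpoint meant to describe the frequency and severity of TEAEs and the withdrawals they cause. In a first-in-human study with four active participants per dose level, one such event is visible in the tables.

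**Working it through.** The plan states no figure on this point and tests no hypothesis, so there is nothing to reproduce. The check is a reading of the rules together, followed by arithmetic for scale.

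**Step 1: which worsening events are flagged?**

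| Situation | How it is recorded | Flagged under SAP 3.5.1? |
|---|---|---|
| Chronic or intermittent preexisting condition worsens after dosing, entered as a new event dated at the worsening | New record (Appendix 3, 10.3.1) | Yes |
| The same, but entered with the original onset date | Neither document says which start date applies | No |
| Event begins between consent and the first dose date, then worsens after dosing | Update to the original record (Appendix 3, 10.3.3) | No, if the start date is kept |
| Event begins on the dosing day before the dose | Depends on whether a time was collected | Can be flagged if no time was collected |

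The gap is mainly the third row, together with any case in the second.

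**Step 2: which outputs use the flag?** Only the TEAE component does. Laboratory, vital sign and ECG endpoints have their own pre-dose baselines (SAP Sections 3.5.2 to 3.5.4). The escalation and stopping rules in Protocol Section 6.6.1 refer to adverse events and abnormalities, not to the TEAE flag.

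**Step 3: where does it fall?** PART-2 is parallel, so any cohort can be affected. In PART-1, PART-3 and PART-5 the first dose comes in Period 1. For the gap to matter in a later period, an event would have to begin before Period 1, persist through the washout (at least 5 days in PART-1 and PART-5, at least 2 in PART-3) and then worsen. In PART-1 the exposed dose levels are therefore mainly D1 and D2 (protocol table of the provisional PART-1 dosing scheme). In PART-5 one of the two sequences receives placebo in Period 1.

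**Step 4: effect of one missed participant.** The change in group incidence is 100/n percentage points, with group sizes from Protocol Sections 9.2.1, 9.2.2 and 9.2.5:

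- 4 active participants (a PART-1 dose level or a PART-2 cohort): 100/4 = 25.0
- 2 placebo participants (same groups): 100/2 = 50.0
- 12 participants in PART-5: 100/12 = 8.3; with 10 completers, 100/10 = 10.0

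**Step 5: chance that it happens at all.** The documents give no rate, so p, the probability that a participant has such an event, is an assumption. The maximum for the three parts with a primary safety endpoint is 12 + 30 + 12 = 54. The expected number is 54p, and P(at least one) = 1 − (1 − p)^54.

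| Assumed p | Expected number | P(at least one) |
|---|---|---|
| 1% | 0.54 | 0.42 |
| 2% | 1.08 | 0.66 |
| 5% | 2.7 | 0.94 |
| 10% | 5.4 | 0.997 |

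These are upper-end counts for each p. They treat all 54 as distinct people, although PART-2 participants may enter PART-5, and they take no account of the narrower Period 1 exposure in Step 3.

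**The case against.** The strongest defence is that the step from Appendix 3 to a retained start date is an inference. The follow-up provision does not mention severity changes, start dates or splitting of events. The CRF completion instructions and the sponsor's reporting standards are not in the documents and may deal with worsening. This stands as a limit: the event can be lost, not must be lost. It does not remove the point, because a worsening rule held elsewhere would contradict the explicit closing sentence of Section 3.5.1, and that sentence would still need changing.

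The practical consequence is also limited. Every adverse event is recorded and reviewed during the study, escalation does not depend on the flag, and no test is planned. Further, the protocol counts ritonavir as study intervention (Section 6). If the ritonavir dose given about 12 hours before PF-07321332 is the first dose, the pre-dose window is shorter.

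A reader might infer more than the documents support:

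- *Every pre-dose event that worsens is dropped.* Section 10.3.1 makes an exacerbation of a chronic or intermittent condition an adverse event in its own right. Entered with its own date, it is flagged.
- *The rule makes the drug look safer than placebo.* It applies to placebo as well, where one missed event moves incidence by 50 points against 25 on active treatment. Only the fall in absolute counts has a known direction.
- *The rule also loses an event that starts in a placebo period and worsens in a later active period.* That event began after the first dose, so the closing sentence does not exclude it. Attribution of events to periods is a separate question.

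**Conclusion.** The point holds in a limited form and should be corrected. As written, SAP Section 3.5.1 can omit from the TEAE tables an adverse event that was recorded between consent and first dose and then became more severe or serious after dosing. That touches one component of the primary endpoint in PART-1, PART-2 and PART-5 and a secondary endpoint in PART-3 and PART-4.

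The conclusion rests on one assumption: that a worsening is entered in the existing record with its start date unchanged, which is the natural reading of Appendix 3 but is not spelled out. Given that, absolute TEAE counts can only be too low. Each affected participant shifts a small group's incidence by the amounts in Step 4. The number affected cannot be derived from the documents, and the effect on the active-placebo comparison has no known direction.

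**What to change.** Replace the closing sentence of SAP Section 3.5.1 with:

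> Events that started before the first dose are not TEAEs unless they increase in severity or become serious on or after the first dose; such an event is counted once, at its post-dose severity, under the treatment during which it worsened. If the worsening was entered as a separate AE record, only that record is flagged.

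The last sentence of this text prevents double counting where a site has already opened a new record for the worsening.

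The cost is a short SAP change and some programming. A few more events will count as TEAEs. The date of worsening must be taken from the adverse event record, so the data should be checked for it first. SAP version 2.0 already reports changes made after table review, so the SAP version history should state when this rule was added and why.
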